7.1.2. Secondary Endpoints

The secondary endpoints include:

1. TTCW, the time (in days) from start of treatment to first event (first day the event is noted), with iNO as compared to placebo, measured from baseline to 18 weeks. TTCW event is defined as any of the following:
 - a. Death (all-cause mortality)
 - b. Atrial septostomy
 - c. Hospitalization due to worsening of PAH (adjudicated)
 - d. Start of new specific PAH treatment (endothelin receptor antagonists [ERAs], phosphodiesterase type-5 [PDE-5] inhibitors or prostanoids), an increase in the dose of an ERA or PDE-5, increase in the dose or frequency of an inhaled prostanoids, or an increase in the dose of an intravenous or subcutaneous prostanoids by >10%.
 - e. Decrease of >15% from baseline or >30% compared with the last study related measurement in 6MWD should be confirmed by a repeat measurement performed at least 14 days later
 - f. Worsening of WHO Functional Class (e.g., from Class II to Class III or IV, OR Class III to Class IV); and should be confirmed by a repeat assessment at least 14 days later
2. Change in WHO Functional Class, with iNO as compared to placebo, from baseline to 18 weeks

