10.1. Subject Discontinuation from Study Drug/Device

Any subject who is discontinued from the study drug will be encouraged to perform all procedures and assessments as appropriate until week 18. Vital status will be determined at the EOS on all subjects who prematurely discontinue. The specific reason for discontinuation will be documented in the eCRF. Subjects may be discontinued due to the following:

1. In the opinion of the Investigator, it is in the subject's best interests to discontinue study drug.
2. Subject no longer wishes to continue using the drug/device.
3. A subject becomes pregnant.
4. In the opinion of the Investigator, the subject experiences clinically significant rebound PH temporally associated with acute withdrawal of study drug.
5. If a subject experiences any of the following: death, atrial septostomy, lung or heart-lung transplantation.

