11.1.25. Lung Transplantation Listing Status

Subjects on active lung transplant lists will be recorded in the eCRF. At each study visit in Part 1, including early discontinuation, the status of the subject on an active lung transplant list (i.e., not on list, on active list, undergone lung transplantation, removed from active list, died while awaiting transplant) will be recorded in the eCRF. If the subject is removed from an active transplant list during the study, the reason for removal must be recorded in the eCRF. Vital status

must be determined 30 days after lung transplantation. Lung transplant assessments will not be performed in Part 2.

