**Table 4: Time Clinical Worsening Event Derivation**

Variables	Module	Source of Data	Derivation	Comments (to be removed later)
All-cause mortality	End of Therapy Status SAE	CRF	One-One mapping	Standard binary field
Atrial septostomy	End of Therapy Status	CRF	One-One mapping	Standard Binary field
Hospitalization due to worsening of PAH (adjudicated)	Adjudication Module	Non CRF	One-One mapping	Standard Field
New PAH treatment	PAH specific therapies	CRF	One-One mapping	Refer to new PAH Therapy Module
Decrease of >15% from baseline or >30% compared with the last study related measurement in 6MWD should be confirmed by a repeat measurement performed at least 14 days later	6 minute walk test	CRF	
1) Decrease of >15% from Baseline
 
Or
 
2) Greater than 30% compared with baseline
 
And
 
3) should be confirmed by repeat
	
Points (1) and (2) are simple derivations ;
 
Point (3) is linked to visit window mapping, so be careful.

Variables	Module	Source of Data	Derivation	Comments (to be removed later)
			measurement performed at least 14 days	
Worsening of WHO Functional Class (e.g., from Class II to Class III or IV, OR Class III to Class IV); and should be confirmed by a repeat assessment at least 14 days later	WHO functional class assessment done at every visit, choose only post baseline	CRF	(1) Class II to class III (2) Class III to class IV (3) Confirmation by repeat assessment at least 14 days later	Points (1) and (2) are simple derivations ;  Point (3) is linked to visit window mapping, so be careful.

2. Change in World Health Organization (WHO) Functional Class (Table 5 and Table 6) from baseline to 18 weeks

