**Table 15: Lung Transplants**

Variables	Module	Source of Data	Variable specific derivation	Derivation	Comments(to be deleted later)
Lung Transplant status	Total Lung Capacity (TLC)	CRF	No, CRF data.	No.	

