Patient Reported Outcome (SF-36)		X					X	X
AE's/SAE's/AESI's		X	X	X	X	X	X	X
Drug Dispensing for Run-in period		X l						
Drug Dispensing for Treatment period			X l	X l	X l	X l	X l	

Assessment	Screening	Run-in		Blinded Treatment Period				
Drug Device Usage a			X n	X n	X n	X n	X n	X n
INOpulse questionnaire							X m	X
Survival Assessment			X	X	X	X	X	X
Medical Resource Utilization	X	X	X	X	X	X	X	X
Lung Transplantation Listing Status	X	X	X	X	X	X	X	X

a: A Screening 6MWT may be obtained at baseline if the subject is known to have a 6MWD  $\geq 100$  meters and  $\leq 450$  meters. The average of two 6MWD at Week 2 after run-in will be used at the baseline.

b: Total lung capacity test to be done if not performed within 6 months of screening.

c: DLCO (Diffusing Capacity for Lungs Measured Using Carbon Monoxide) will be performed at Screening Only.

d: Height and Weight to be performed at Screening.

e: N/A-Footnote no longer applicable as of Amendment #3

f: Pregnancy test to be performed at the discretion of investigator.

g: N/A-Footnote no longer applicable as of Amendment #3.

h: Subjects will be required to demonstrate an average daily usage  $\geq 12$  hours (rounded to the nearest hour) with no more than 2 days of usage  $< 8$  hours per day of the INOpulse device during the initial 2 weeks of the study in order to be eligible to continue to the treatment phase.

i: RHC should be obtained at early discontinuation only for subjects participating in RHC substudies ECHO should be obtained for all subjects at early discontinuation regardless if they are participating in the ECHO substudy.

j: A RHC will be conducted at Screening for subjects who are not included in this subset who have not had a RHC within the previous 5 years that meet eligibility criteria and are otherwise eligible.

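### The WHO-class derivation cell in SAP Table 4 omits II to IV, which its own row includes; separately, and of less weight, Table 15 takes transplant status from a Screening-only module

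*SAP*

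**What the plan says.** **WHO class.** SAP 4.2 points to Tables 3 and 4 for the definition of a clinical worsening event. In Table 4, the variable cell of the WHO row reads "Worsening of WHO Functional Class (e.g., from Class II to Class III or IV, OR Class III to Class IV", followed by the requirement of a repeat assessment. The derivation cell of that row reads "1) Class II to class III (2) Class III to class IV (3) Confirmation by repeat assessment at least 14 days later", and the comment beside it calls the first two items simple derivations. Protocol 7.1.2 gives the criterion as worsening of class, "e.g., from Class II to Class III or IV, OR Class III to Class IV". SAP Table 3 (criterion 6) and SAP 7.4.1 use the same wording as the protocol. SAP 7.4.1 and Table 26 also analyse time to WHO worsening on its own. The baseline class is the Week 2 assessment (SAP Table 6 and 6.4).

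**Transplant status.** SAP Table 15 gives the source module for lung transplant status as "Total Lung Capacity (TLC". The notes to the SAP's Part I schedule say of that test: "Total lung capacity test to be done if not performed within 6 months of screening". Protocol 11.1.25 describes a different record, kept in the eCRF: "At each study visit in Part 1, including early discontinuation, the status of the subject on an active lung transplant list". Its categories include having undergone lung transplantation and having died while waiting. Protocol 10.1 also lists, among the reasons for stopping study drug, "If a subject experiences any of the following: death, atrial septostomy, lung or heart-lung transplantation", and requires the specific reason to be entered in the eCRF.

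**The concern.** Table 4 is the part of the SAP that a programmer would code from, and SAP 4.2 makes it part of the event definition. For WHO class its derivation column is narrower than the criterion beside it, and the change left out is the largest one. The column cannot simply be assumed to follow the definition: in the row above, the 30% fall in 6MWD is set against baseline, while the criterion sets it against the last study measurement.

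TTCW is tested under type 1 error control directly after 6MWD. If the contradiction is still open at unblinding, someone must then decide which subjects had an event and on what date. In the composite, another criterion may still capture the subject. In the stand-alone WHO analysis nothing else can.

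Table 15 is a separate matter. It is the only source that SAP 4.3 states for the transplant variables of tertiary endpoint 8. It names a lung-function test that is not scheduled at any visit where an on-study transplant could be seen.

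**Working it through.** The plan states no figure on this point, so there is none to reproduce. The check is an enumeration.

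**1. Class changes.** Eligible classes are II, III and IV.

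- Worsenings under the definition: II to III, II to IV, III to IV (3).
- Worsenings in the Table 4 derivation cell: II to III, III to IV (2).
- Difference: II to IV only, so the cell covers 2 of 3.

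**2. Visit paths.** Classes are shown at Weeks 2 (baseline), 6, 10, 14 and 18. Two assumptions are made. Under the definition, an event is confirmed if the next visit still shows a class above baseline. Under the literal reading, the change from baseline must be one of the two listed.

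| Path | Definition | Table 4 cell, read literally |
|---|---|---|
| II-IV-IV-IV-IV | event at Week 6 | no event |
| II-II-II-IV-IV | event at Week 14 | no event |
| II-IV-III-III-III | event at Week 6 | event at Week 10 (10 − 6 = 4 weeks later) |
| II-III-III-IV-IV | event at Week 6 | event at Week 6 |
| III-IV-IV-IV-IV | event at Week 6 | event at Week 6 |
| II-III-IV-IV-IV | event at Week 6 | depends on whether Class IV may confirm a move to Class III |

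Direct falls from II to IV are therefore lost or delayed. A subject with a confirmed Class III on the way is counted under both readings. The last path is open because the cell does not say what class confirms a change. A fall first seen at Week 18 has no later scheduled Part 1 visit to confirm it, so the cell makes no practical difference there.

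**3. Collection points for transplant status** (Protocol Table 2, Part 1).

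- Total Lung Capacity: Screening only, and only if there is no test within 6 months. Points after Screening: 0.
- Listing status: Weeks 0, 2, 6, 10, 14, 18 and early discontinuation. Points after Screening: 7.

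**4. Coverage of the endpoint.** SAP 4.3 item VIII counts heart-lung or lung transplants. The listing-status item is described as "the status of the subject on an active lung transplant list (i.e., not on list, on active list, undergone lung transplantation" and names lung transplantation only. Protocol 10.1 names both. Neither record alone clearly covers the endpoint, so both are needed.

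**The case against.** The strongest reply is that Table 4 contains an incomplete abbreviation and not a rule. The variable cell of the same row, Table 3, SAP 7.4.1, Table 26 and the protocol all name II to IV, and all give the class changes as examples of worsening. Table 4 still carries a comments column marked for later removal, so it looks like a working table. This stands to the following extent. A reader might infer that the SAP excludes a two-class fall from TTCW. The documents do not support that: one cell contradicts its own row and every other statement. But SAP 4.2 gives Table 4 defining force, so the contradiction has to be resolved.

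The reach is also narrow, as the paths show, and other TTCW criteria may capture the same subjects. That is accepted. A reader might further infer that the missed subjects are the sickest. That is not supported either: a subject who goes from III to IV ends in the same class and is counted. Two classes is the largest change, not a worse end state.

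On Table 15, a reader might infer that every on-study transplant would be missed, or that the count would be zero in both arms. The documents do not show this. No eCRF specification is included, so the content of the module cannot be checked. A module without a transplant field would more likely make the program fail visibly than return false zeros. SAP 4.3 item VIII states the intended variables correctly, and the data are collected elsewhere. What stands is that the named source is wrong as written.

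**Conclusion.** Both slips are real, and they differ in weight.

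The Table 4 cell contradicts the definition of a type-1-error-controlled secondary endpoint. Coded literally, it misses a direct confirmed II-to-IV fall, or dates it later if the subject then moves to Class III, in TTCW and in the separate time-to-WHO-worsening analysis. The documents give no rate of such falls, so the effect on the results cannot be sized. It is probably small. The reason to act is that the choice should not be left open until after unblinding.

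The Table 15 mapping is a lesser error. Transplantation is not one of the six TTCW criteria in SAP Table 3. The endpoint it serves is tertiary and carries no multiplicity adjustment (SAP 7.6).

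The conclusion assumes that the tables are programmed as written, and that the eCRF holds transplant status where Protocol 11.1.25 and 10.1 say it is recorded.

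**What to change.** - **Table 4, WHO row.** Replace the derivation by: any post-baseline class higher than the Week 2 class, confirmed by an assessment at least 14 days later that is also higher than the Week 2 class. This matches the stated definition, covers 3 of 3 worsenings, and settles which class confirms a change.
- **Table 15.** Replace the module by the lung transplantation listing status data collected at each Part 1 visit (Protocol 11.1.25), plus the discontinuation reason that records lung or heart-lung transplantation (Protocol 10.1). That reason is listed together with death and atrial septostomy, so check that the eCRF entry tells them apart.

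The cost is an edit to two table cells, with no new data collection and no change of method. Make it before programming and before unblinding.

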**Table 5: WHO Functional Class**

Class	Subject Symptoms
Class I*	Patients with pulmonary hypertension but without resulting limitation of physical activity. Ordinary physical activity does not cause undue dyspnea or fatigue, chest pain or near syncope.
Class II	Patients with pulmonary hypertension resulting in slight limitation of physical activity. They are comfortable at rest. Ordinary physical activity causes undue dyspnea or fatigue, chest pain, or near syncope.
Class III	Patients with pulmonary hypertension resulting in marked limitation of physical activity. They are comfortable at rest. Less than ordinary activity causes undue dyspnea or fatigue, chest pain, or near syncope.
Class IV	Patients with pulmonary hypertension with inability to carry out any physical activity without symptoms. These patients manifest signs of right heart failure. Dyspnea and/or fatigue may even be present at rest. Discomfort is increased by any physical activity. Syncope or near syncope may occur.

\*Only subjects with WHO Class II – IV are eligible for the study.

The WHO functional class collected at all the visits.

**Table 6: WHO Functional Class**

Variables	Module	Source of Data	Baseline Definition	Variable specific derivation	Change from Baseline analysis	Comment (to be removed later)
WHO Functional Class Status	WHO Functional Class assessment	CRF	Week 2 (V2) Assessment	No, CRF data.	Yes	This is not Continuous data

For the second part of the study, change in WHO functional class data from Baseline (week 2) and from week 18 will be analysed at month 4, 8 and 12.

### 4.3 Tertiary Efficacy endpoint

#### I. SF-36 V2

Change in health-related quality of life (using SF-36 version 2 health survey) from baseline to 18 weeks.

SF-36 v2 is collected at baseline (v1), Week 18 and at early discontinuation visit during double blind period of study.

The following eight categories are derived from SF-36 v2 ([Table 7](#) and [Table 8](#)) as follows.

**Table 7: SF-36 V2 Categories**

	Category
1	Physical Functioning (PF)
2	Role- Physical (RP)
3	Bodily Pain (BP)
4	General Health (GH)
5	Vitality (VT)
6	Social Functioning (SF)
7	Role-Emotional (RE)
8	Mental Health (MH)

**Table 8: SF-36 V2**

Variables	Module	Source of Data	Baseline Definition	Variable specific derivation
SF-36 v2 questionnaire	SF-36	Non-CRF Data	Baseline (V1)	No, non - CRF data.

## II. Right Heart Catheterization (RHC)

Change in pulmonary hemodynamics measured by right heart catheterization (RHC) (Table 9) from baseline to 18 weeks, in a subset of subjects (approximately 50), at selected site:

1. Cardiac output [CO],
2. Cardiac index [CI] (to be derived),
3. Mean pulmonary artery pressure [mPAP],
4. Mean pulmonary capillary wedge pressure [mPCWP],
5. Systolic pulmonary artery pressure [sPAP],
6. Diastolic pulmonary artery pressure [dPAP],
7. Pulmonary vascular resistance [PVR],
8. Pulmonary vascular resistance [PVR] Index,
9. Oxygen saturation by pulse oximeter [SpO2],
10. Mixed venous O2
11. Right atrial pressure [RAP],

**Table 9: Pulmonary Hemodynamic Measured by Right Heart Catheterization (RHC)**

Variables	Module	Source	Continuous/ Categorical	Baseline Definition	Variable specific derivation	Change from Baseline analysis
Cardiac Output (CO)	RHC	CRF	Continuous	Baseline (V1)	No, CRF data.	Yes
Cardiac Index (CI)	RHC	CRF	Continuous	Baseline (V1)	CI = CO/BSA ; BSA = 0.007184*(weight 0.425 )*(Height 0.725 )	Yes
Mean Pulmonary artery pressure (mPAP)	RHC	CRF	Continuous	Baseline (V1)	No, CRF data.	Yes
Mean Pulmonary Capillary wedge pressure (mPCWP)	RHC	CRF	Continuous	Baseline (V1)	No, CRF data.	Yes
Systolic pulmonary artery pressure	RHC	CRF	Continuous	Baseline (V1)	No, CRF data.	Yes

Variables	Module	Source	Continuous/ Categorical	Baseline Definition	Variable specific derivation	Change from Baseline analysis
(sPAP)						
Diastolic pulmonary artery pressure (dPAP)	RHC	CRF	Continuous	Baseline (V1)	No, CRF data.	Yes
Pulmonary vascular resistance (PVR),	RHC	CRF	Continuous	Baseline (V1)	No, CRF data.	Yes
Pulmonary vascular resistance [PVR] Index	RHC	CRF	Continuous	Baseline (V1)	$PVR \text{ (Index)} = 80 \text{ (mPAP - mPCWP)} \div CI$	
Oxygen saturation by pulse oximeter (SpO2)	RHC	CRF	Continuous	Baseline (V1)	No, CRF data.	Yes
Mixed venous O2	RHC	CRF	Continuous	Baseline (V1)	No, CRF data.	Yes
Right atrial pressure (RAP)	RHC	CRF	Continuous	Baseline (V1)	No, CRF data.	Yes

### III. Echocardiogram

Changes in the right and left ventricular function by echocardiography will be analysed by cardiac imaging core laboratory at the Brigham and Women's Hospital.

### IV. NT-proBNP:

Change in NT-proBNP (Table 10) from screening to 18 weeks.

**Table 10: NT-proBNP**

Variables	Module	Source of Data	Continuous/ Categorical	Baseline Definition	Variable specific derivation	Change from Baseline analysis
NT-proBNP	Lab	Non CRF	Continuous	Screening (V0)	No, CRF data.	Yes

**V. Borg Dyspnea Score:**

Change in Borg dyspnea score (Table 11 and Table 12) immediately following 6MWT from baseline to 18 weeks for blinded period and change from baseline and from week 18 at month 4, 8 and 12 during open label period of study.

The Borg Dyspnea score defined as follows:

**Table 11: Borg Dyspnea Score**

Score	Severity
0	Nothing at all
0.5	Very, very slight (just noticeable)
1	Very slight
2	Slight (light)
3	Moderate
4	Somewhat severe
5	Severe (heavy)
6	--
7	Very Severe
8	--
9	--
10	Very, very severe (maximal)

**Table 12: Borg Dyspnea Score**

Variables	Module	Source of Data	Baseline Definition	Variable specific derivation	Change from Baseline analysis
Borg dyspnea score	Six Minute Walk Test (SMWT)	CRF	Week 2 (V2) Assessment	No, CRF data.	Yes

**VI. 6MWD and Drug Adherence:**

Change in 6MWD as related to degree of drug adherence (Table 13) from baseline to 18 weeks.

The drug adherence categories defined as follows:

- 1) Average Compliance < 8 hours per day
- 2) Average Compliance  $\geq$  8 hours per day
- 3) Average compliance < 12 hours per day
- 4) Average Compliance  $\geq$ 12 hours per day
- 5) Average Compliance  $\geq$ 16 hours per day

**Table 13: 6MWD and Drug Adherence**

Variables	Module	Source of Data	Baseline Definition	Variable specific derivation	Change from Baseline analysis
6MWD	Six Minute Walk Test (SMWT)	CRF	Week 2 (V2) Assessment	Derived variable for average compliance	Yes
Drug Adherence	Drug Compliance assessment from Y-Prime	Non CRF			

**VII. Clinical Response:**

Number of subjects with unsatisfactory clinical response (Table 14), (WHO Functional Class III or IV symptoms with no improvement in 6MWD), with iNO as compared with Placebo, from baseline to 18 weeks.

**Table 14: Clinical Response**

Variables	Module	Source of Data	Variable specific derivation	Combined Derivation
WHO Functional Class Status	WHO Functional Class assessment	CRF	No, CRF data.	At week 18 WHO status is III or IV.
6MWD	Six Minute Walk Test (SMWT)	CRF	No, CRF data.	1) Decrease of >15% from baseline Or 2) Greater than 30% compared with baseline And should be confirmed by repeat measurement performed at least 14 days

**VIII. Lung Transplants:**

The following variables will be summarized and analyzed in context to lung transplant (Table 15) between the treatments, from baseline to 18 weeks.

- 1) Number of subjects undergoing heart-lung or lung transplant
- 2) Number of deaths while awaiting transplantation (at the beginning of the study)
- 3) Number of subjects on transplant list at the beginning of study

- 4) Number of subjects on transplant list during the study

**Table 15: Lung Transplants**

Variables	Module	Source of Data	Variable specific derivation	Derivation	Comments(to be deleted later)
Lung Transplant status	Total Lung Capacity (TLC)	CRF	No, CRF data.	No.	

**IX. Number of Hospitalizations:**

The number of PAH specific hospitalizations (Table 16) will be summarized and analyzed between the treatment.

**Table 16: Number of Hospitalizations**

Variables	Module	Source of Data	Variable specific derivation	Derivation	Comments(to be deleted later)
Hospitalization Status	Additional Inpatient Hospitalization (AIPH)	CRF	No, CRF data.	No.	

**X. Medical Resource Utilization:**

Analysis of Medical Resource Utilization from MDRU panel.

## 4.4 Safety Endpoint

The secondary endpoint in this study part I includes:

- 1) Incidence and severity of adverse events (AEs)
- 2) Incidence of device malfunction and/or device failure leading to an AE
- 3) Incidence of rebound pulmonary hypertension (PH)
- 4) Clinically significant changes in:
  - a. Clinical laboratory tests
  - b. Pulmonary function tests
  - c. Vital signs

For study part II primary endpoint is incidence of AEs and SAEs.

## 5.0 Study Design

### 5.1 General Design and Plan

[figure not shown]
This is a multi-center, randomized, double-blind, placebo-controlled, parallel-group design to determine the efficacy, safety and tolerability of pulsed iNO versus placebo in symptomatic subjects with PAH currently receiving background PAH medication and LTOT.

The study consists of two parts Part 1, the Blinded Treatment Period, and Part 2, the Open Label Extension Period. The duration of treatment in double blind period will be a maximum of 18 weeks. Subjects will be offered open label therapy when a subject completes 18 weeks of blinded drug therapy.

Screen failures will be defined as subjects who sign the ICF but fail to meet the eligibility criteria and/or do not qualify for randomization.

Subjects who do not complete their scheduled visits, have not died, and have not officially withdrawn from the study are considered lost to follow-up.

